2.19 Biomarkers

Not applicable.

2.21 Interim analysis

Not applicable.

3 Sample size calculation

Existing data suggest that the difference between LCZ696 and enalapril in VO_{2peak} at month 3 may be about $1.5 \text{ mL kg}^{-1} \text{ min}^{-1}$ with a (common) SD of 3 (Guazzi et al. 1999; Lewis et al. 2007). Under these assumptions, 86 patients per treatment arm would be required to achieve 90% power on a 2-sided, 5% significance level. To compensate for some drop-out and other protocol deviation 100 patients per treatment group (200 in total) will need to be enrolled into this trial. The above mentioned literature suggests that the treatment effect for the key secondary endpoint, VO_{2peak} after 6 weeks, might be of a similar magnitude, therefore, the sample size calculation above applies also for the key secondary endpoint.

4 Change to protocol specified analyses

VO_{2peak} adjusted to body weight will be calculated as follows for the analysis:

$$VO_{2peak} \text{ (adjusted)} = \frac{VO_{2peak} \text{ (unadjusted)}}{\text{Body weight}}$$

VO_{2peak} (adjusted) will be calculated at visit 2, 6 and 7 based on the visit's VO_{2peak} (unadjusted) and body weight data.

Note1: The collected data of VO_{2peak} adjusted will remain as it is in source data.

Note2: Patient [REDACTED] was unblinded at site on [REDACTED] for safety purpose. However, as confirmed by CTT, the patient would not be excluded from the analyses.

5 Appendix

Appendix 1: Clinically notable laboratory values

Clinically notable laboratory abnormalities for selected tests based on a percent change from baseline:

Hematology

- RBC count >50% increase, >20% decrease
- Hemoglobin >50% increase, >20% decrease
- Hematocrit >50% increase, >20% decrease
- WBC count >50% increase, >50% decrease
- Platelet count >75% increase, >50% decrease

Blood Chemistry

- ALT (SGPT) >150% increase
- AST (SGOT) >150% increase
- BUN >50% increase
- Creatinine >50% increase
- Total bilirubin >100% increase
- CPK >300% increase
- Alkaline phosphatase >100% increase
- Potassium >20% increase, >20% decrease
- Chloride >10% increase, >10% decrease
- Calcium >10% increase, >10% decrease
- Uric acid >50% increase

Appendix 2: Liver event definitions and follow-up requirements

Table 19-1 Liver event definitions

	Definition/
Adverse event of special interest	
Laboratory values	ALT or AST > 3 x ULN ALP TBL >

Medically significant event (SAE)

Laboratory values	
ALT or AST > 5 x ULN (with or without TBL > 2 x ULN [mainly conjugated fraction])
 
ALP > 5 x ULN (with or without TBL > 2 x ULN [mainly conjugated fraction])
 
TBL
 
Potential Hy's Law cases (defined as ALT/AST > 3 x ULN and TBL > 2 x ULN [mainly conjugated fraction] without notable

Adverse events	
Any clinical event of jaundice (or equivalent term)
 
ALT or AST > 3 x ULN accompanied by general malaise, fatigue, abdominal pain, nausea, or vomiting, or
 
Any event that links to a preferred term (PT) in the MedDRA dictionary falling under the SMQ sub-module "Drug-related hepatic disorders – severe events only"* or

* These events cover the following: hepatic failure, fibrosis and cirrhosis, and other liver damage-related conditions; the non-infectious hepatitis; the benign, malignant and unspecified liver

Table 19-2 Liver event follow up requirements

Criteria	Event	Actions required	Follow-up monitoring
Potential Hy's Law case ^a	Medically significant	
Discontinue the study drug immediately
 
Hospitalize, if clinically appropriate
 
Report to Novartis as an SAF
 
Establish causality
	
ALT, AST, TBL, Alb, PT, ALP and γGT until resolution^c (frequency at investigator discretion)

ALT or AST			
> 8 x ULN	Medically significant	
Repeat LFT within 48 hours
 
If elevation persists, discontinue the study drug immediately
 
Hospitalize if clinically appropriate
 
Report to Novartis as an
	
ALT, AST, TBL, Alb, PT, ALP and γGT until resolution^c (frequency at investigator discretion)

> 5 to ≤ 8 x ULN	Medically significant	
Repeat LFT within 48 hours
 
If elevation persists for more than 2 weeks, discontinue the study drug
 
Report to Novartis as an
	
ALT, AST, TBL, Alb, PT, ALP and γGT until resolution^c (frequency at investigator discretion)

> 3 x ULN accompanied by symptoms ^b	Medically significant	
Discontinue the study drug immediately
 
Hospitalize if clinically appropriate
 
Report to Novartis as an
 
SAF
 
Establish causality
	
ALT, AST, TBL, Alb, PT, ALP and γGT until resolution^c (frequency at investigator discretion)

> 3 to ≤ 5 x ULN (patient is asymptomatic)	AESI	Central laboratory to report to Investigator & Novartis Repeat LFT once or twice in the week If elevation persists	Investigator discretion Monitor LFT within 1 to 4 weeks or at next visit
≤ 3 x ULN (patient is asymptomatic)	N/A	Repeat LFT at next visit	
ALP (isolated)			
> 5 x ULN	Medically significant	Repeat LFT within 48 hours If elevation persists, report to Novartis as an SAE	Investigator discretion Monitor LFT within 1 to 4 weeks or at next visit
> 2 to ≤ 5 x ULN (patient is asymptomatic)	AESI	Central laboratory to report to Investigator & Novartis Repeat LFT once or twice in the week. If elevation	Investigator discretion Monitor LFT within 1 to 4 Weeks or at next visit
≤ 2 x ULN (patient is asymptomatic)	N/A	Repeat LFT at next visit	
TBL (isolated)			
> 3 x ULN	Medically significant	Repeat LFT within 48 hours If elevation persists, discontinue the study drug immediately Hospitalize if clinically appropriate Report to Novartis as an SAE Establish causality	ALT, AST, TBL, Alb, PT, ALP and γGT until resolution (frequency at investigator discretion) Test for hemolysis (e.g., reticulocytes, haptoglobin, unconjugated [indirect] bilirubin)
> 1.5 to ≤ 3 x ULN (patient is asymptomatic)	AESI	Central laboratory to report to Novartis Repeat LFT once or twice in the week If elevation persists, establish causality	investigator discretion Monitor LFT within 1 to 4 weeks or at next visit
≤ 1.5 x ULN (patient is asymptomatic)	N/A	Repeat LFT at next visit	
Preferred terms			

Jaundice	Medically significant	Discontinue the study drug immediately Hospitalize the patient Report to Novartis as an SAE Establish causality	ALT, AST, TBL, Alb, PT, ALP and γ GT until resolution ^c (frequency at investigator discretion)
“Drug-related hepatic disorders - severe events only” SMQ AE	Medically significant	Discontinue the study drug hospitalization if clinically appropriate Report to Novartis as an SAE Establish causality	Investigator discretion

^a Elevated ALT/AST > 3 x ULN and TBL > 2 x ULN but with no notable increase in ALP to > 2 x ULN

^b General malaise, fatigue, abdominal pain, nausea, or vomiting, rash with eosinophilia

^c Resolution is defined as an outcome of one of the following: return to baseline values, stable values at three subsequent monitoring visits at least 2 weeks apart, remain at elevated level after a maximum of 6 months, liver transplantation, and death.

Appendix 3: Guidelines for the management of renal dysfunction

General principles:

Glomerular filtration rate in HF patients depends on intrinsic renal function and on a balance between afferent and efferent glomerular arterial tonicity. This tonicity is partly regulated by a stimulation of angiotensin II and could be affected by either study medication. Moreover, renal dysfunction may develop or may deteriorate in some patients after study drug administration. These recommendations have been developed to guide the investigators in managing patients with renal dysfunction after randomization.

Two types of response to serum creatinine increase are described:

Surveillance situation

If, at any time after randomization, eGFR decreases by $\geq 25\%$ from baseline (Visit 2) (or if serum creatinine concentration increase to 2.5 mg/dL [221 μ mol/L]), the investigator will check for potentially reversible causes of renal dysfunction such as:

- Non-steroidal anti-inflammatory drug intake, antibiotics, or other treatments known to affect creatininemia
- Volume decrease, including that resulting from excessive dosing of diuretics
- Urinary infection
- Urinary tract obstruction
- Study medication

Action situation

If a patient eGFR decreases by $\geq 40\%$ from baseline (Visit 2) (or if serum creatinine concentration rises above 3 mg/dL (265 μ mol/L)), the investigator will check for potentially reversible causes of renal dysfunction (see above).

If the investigator judges that study medication has to be stopped, he/she will have to contact the Novartis medical monitor or his/her designee. Thereafter, serum creatinine assessments will have to be repeated at least each week until levels return to acceptable values. If study medication was stopped, every effort will be done to restart it again, according to clinical conditions.

Appendix 4: Treatment guidelines for hyperkalemia (serum potassium greater than or equal to 5.3 mmol/L)

General principles

Elevation of potassium levels above the predefined values should be repeated and confirmed before any action is taken.

Any patient with a serum potassium ≥ 5.3 mmol/L after enrollment into the study requires regular, repeated checks of potassium concentration (beyond that prescribed in the protocol) until it is clear that the potassium concentration is stable and not rising into the range of concern (≥ 5.5 and < 6.0 mmol/L) or potential danger (≥ 6.0 mmol/L).

Patients with elevated potassium value will be managed according to the corrective actions outlined below. Hyperkalemia should be followed until resolution.

Corrective action for management of hyperkalemia

Serum potassium ≥ 5.3 and less than or equal to 5.5 mmol/L

- Confirm potassium concentration in a non-hemolyzed sample
- Reinforce low potassium diet and restriction of food/drinks with high potassium content (e.g. orange juice, melon, bananas, low-salt substitutes etc.)
- Review medical regimen (including dietary supplements and over-the-counter medications) for agents known to cause hyperkalemia. Consider reduction in dose or discontinuation of these agents:
 - Aldosterone antagonists (if they are believed to be the most likely cause of hyperkalemia)
 - Potassium-sparing diuretics (e.g. amiloride and triamterene) including in combination products with thiazide or loop diuretics
 - Potassium supplements, e.g., potassium chloride
 - Salt substitutes
 - Non-steroidal anti-inflammatory drugs (NSAIDs)
 - Cyclo-oxygenase-2 (COX-2) inhibitors
 - Trimethoprim and trimethoprim-containing combination products, such as trimethoprim/sulfamethoxazole fixed combinations
 - Herbal Supplements:

- For example, Noni juice, alfalfa (*Medicago sativa*), dandelion (*Taraxacum officinale*), horsetail (*Equisetum arvense*), nettle (*Urtica dioica*), milkweed, lily of the valley, Siberian ginseng, hawthorn berries
- Repeat serum potassium measurement within 3 to 5 days
- If serum potassium remains ≥ 5.3 and ≤ 5.5 mmol/L, regularly monitor serum potassium levels to ensure stability (suggested once monthly)
- Consider down-titration of study medication, according to investigator's medical judgment.

Serum potassium > 5.5 and < 6.0 mmol/L

- Confirm potassium concentration in a non-hemolyzed sample
- Consider down-titration or temporarily discontinue study drug according to investigator medical judgment.
- Apply all measures outlined for serum potassium ≥ 5.3 and ≤ 5.5 mmol/L
- Repeat serum potassium measurement after 2-3 days
- If serum potassium < 5.5 mmol/L, consider resumption of study drug at lower dose with repeat potassium within 5 days

Serum potassium greater than or equal to 6.0 mmol/L

- Immediately discontinue study drug
- Confirm potassium concentration in a non-hemolyzed sample
- Urgently evaluate patient and treat hyperkalemia as clinically indicated
- Apply all measures outlined for serum potassium ≥ 5.3 and < 6.0 mmol/L

No resumption of study drug without individualized case discussion with and permission from Novartis medical monitor or his/her designee.

5.1 Imputation rules

5.1.1 Study drug

Not applicable.

5.1.2 AE date imputation

Date imputation for AEs will be imputed according to Novartis conventions described in [\[RAP Module 8\]](#).

AE Start Date Imputation (#IMPUTAEV)

This algorithm is expressed in the Variable Source Derivation column as #IMPUTAEV (*event*) where *event* is the partial date of the adverse event.

The following table explains the notation used in the logic matrix. Please note that **missing start dates** will not be imputed.

	Day	Month	Year
Partial Adverse Event Start Date	Not used	MON	YYYY
Treatment Start Date(TRTSTD)	Not used	TRTM	TRTY

The following matrix explains the logic behind the imputation.

	MON MISSING	MON<TRTM	MON=TRTM	MON>TRTM
YYYY MISSING	(NC) Uncertain	(NC) Uncertain	(NC) Uncertain	(NC) Uncertain
YYYY<TRTM	(D) Before Treatment Start	(C) Before Treatment Start	(C) Before Treatment Start	(C) Before Treatment Start
YYYY=TRTM	(B) Uncertain	(C) Before Treatment Start	(A) Uncertain	(A) After Treatment Start
YYYY>TRTM	(E) After Treatment Start	(A) After Treatment Start	(A) After Treatment Start	(A) After Treatment Start

The following table is the legend to the logic matrix.

If AE end date is complete and AE end date < Treatment start date or AE end date is partial and AE imputed end date < Treatment start date, then AE start reference = min (informed consent date, earliest visit date from SV)

Else if AE end date is partial, AE end date ≥ Treatment start date or AE is ongoing , then AE start reference = treatment start date.

Relationship		
Before AE Start reference	Partial date indicates AE start date prior to AE start reference	
After AE Start reference	Partial date indicates AE start date after AE start reference	
Uncertain	Partial date insufficient to determine relationship of AE start date to AE start reference	
Imputation Calculation		
NC/Blank	No convention	

(A)	MAX(01MONYYYY, AE start reference+1 day)	
(B)	AE start reference+1	
(C)	15MONYYYY	
(D)	01JULYYYY	
(E)	01JANYYYY	
Complete date	No date imputation	
If time is captured for the study:
 
Case 1. if AE start date is not equal to AE start reference then do the following: if minutes missing then AESTMF = M and time is imputed to hh:00 if time missing then AESTMF = H and time is imputed to 00:00
 
Case 2: if AE start date = AE start reference then AESTMF = H and time is imputed to treatment start time + 1 hour

Adverse Event End Date Imputation

Imputed date = date part of original date, if complete date

Imputed date = min (visit 299 date, DEC 31, date of death), if month is missing,

Imputed date = min (visit 299 date, last day of the Month, date of death), if day is missing.

Adverse Event End Time Imputation

If the AE end date is complete and time is captured in the study then:

Case 1. if AE end date is not equal to Treatment end date, then do the following:

if minutes missing then time is imputed to hh:00

if time missing then time is imputed to 00:00

Case 2: if AE end date = treatment end date then time is imputed to treatment end time
If the AE end date is partial then end time is imputed to 00:00.

Imputed Date Flag

If year of the imputed date is not equal to YYYY then date flag = Y
else if month of the imputed date is not equal to MON then date flag = M
else if day of the imputed date is not equal to day of original date then date_flag = D
else date flag = null

Imputed Time Flag

If hours of the imputed time is not equal to hours of original time then time flag = H
else if minutes of the imputed time is not equal to minutes of original time then time flag = M
else time flag = null

5.1.3 Concomitant medication date imputation

Date imputation for concomitant medications will be imputed according to Novartis conventions described in [\[RAP Module 8\]](#).

Concomitant medication(CMD) start date imputation (#IMPUMED)

Rules for imputing the CMD start date:

This algorithm is used when *event* is the partial start date of the concomitant medication, non-drug therapy/procedure, or prior anti-neoplastic therapy.

The following table explains the notation used in the logic matrix. Please note that **missing start dates** will not be imputed.

	Day	Month	Year
Partial CM Start Date	Not used	MON	YYYY
Treatment Start Date(TRTSDT)	Not used	TRTM	TRTY

The following matrix explains the logic behind the imputation.

	MON MISSING	MON<TRTM	MON=TRTM	MON>TRTM
YYYY MISSING	(C2) Uncertain	(C1) Uncertain	(C1) Uncertain	(C1) Uncertain

YYYY<TRTY	(D) Before Treatment Start	(A) Before Treatment Start	(A) Before Treatment Start	(A) Before Treatment Start
YYYY=TRTY	(C2) Uncertain	(A) Before Treatment Start	(C1) Uncertain	(B) After Treatment Start
YYYY>TRTY	(E) After Treatment Start	(B) After Treatment Start	(B) After Treatment Start	(B) After Treatment Start

The following table is the legend to the logic matrix.

Relationship	
Before Treatment Start	Partial date indicates CMD start date prior to Treatment Start Date
After Treatment Start	Partial date indicates CMD start date after Treatment Start Date
Uncertain	Partial date insufficient to determine relationship of CMD start date relative to Treatment Start Date
Imputation Calculation	
(A)	15MONYYYY
(B)	01MONYYYY
(C1 or C2)	IF relative reference start = before treatment start THEN TRTSDT-1 ELSE IF relative reference start = ' ' THEN TRTSDT+1
(D)	01JULYYYY
(E)	01JANYYYY

Concomitant medication end date imputation

If not ongoing then -

Imputed date = date part of CMENDTC, if complete date

Imputed date = min(visit 299 date, DEC 31) , if month is missing, (C2, D, E)

Imputed date = min(visit 299 date, last day of the Month) , if day is missing. (A, B, C1)

Concomitant medication date flag

If not a complete date then

Y - If year of the imputed date is not equal to YYYY else

M – If month of the imputed date is not equal to MON else

D

5.1.3.1 Prior therapies date imputation

Not applicable.

5.1.3.2 Post therapies date imputation

Not applicable.

5.1.3.3 Other imputations

5.2 AEs coding/grading

Not applicable.

5.3 Laboratory parameters derivations

Not applicable.

5.4 Statistical models

5.4.1 Primary analysis

For ANCOVA model

```
proc mixed data = a;  
  class TRTN CENTRE;  
  model Estimate = TRTN CENTRE BSL_VO2peak;  
  lsmeans TRTN/om;  
  estimate 'LCZ696 - Enalapril' trtn 1 -1 /cl;  
run;
```

For Mann-Whitney-U-test

In case of deviations from the normality assumptions, treatments will additionally be compared by a non-parametric test (Mann-Whitney-U-test).

```
proc NPAR1WAY data=a wilcoxon;  
  class TRTN CENTRE;  
  var VO2peak;  
  exact wilcoxon;  
run;
```

here VO2peak variable contains change from baseline to Week X.

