9.4.4 Supportive analyses

In case of serious deviations from the normality assumptions, treatments may additionally be compared by a non-parametric test (Mann-Whitney-U-test). In case of a substantial rate of missing data (>15%) or strong imbalances between treatment groups, Multiple Imputation (MI) may be considered as a sensitivity analysis.

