VO ₂	respiratory oxygen uptake
VO _{2max}	respiratory oxygen uptake (max.)
VO _{2peak}	respiratory oxygen uptake (peak)
WBC	White blood cell

[figure not shown]
1 Introduction

The purpose of this document is to provide summary of the statistical methodology that will be used for this clinical study; this includes a detailed description of data summaries. Analysis plans in this document refer to the related statistical analysis sections in clinical study reports.

This Statistical Analysis Plan (SAP) module describes the statistical analysis according to Section 9 of the study protocol along with any additional analyses, specifications or deviations planned.

Data will be analyzed according to the data analysis section 9 of the study protocol which will be available in [Appendix 16.1.1 of the CSR](#). Important information is given in the following sections 2.7 (Analysis of secondary efficacy), 2.8 (Safety evaluation), 2.14 (Interim analysis) and 3 (Sample size calculation).

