2.5.4 Supportive analyses

In case of deviations from the normality assumptions, treatments may additionally be compared by a non-parametric test (Mann-Whitney-U-test). In case of a substantial rate of missing data (>15%) or strong imbalances between treatment groups, Multiple Imputation (MI) may be considered as a sensitivity analysis.

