5.4.2 Key secondary analysis

Key secondary endpoint will be analyzed similarly to the primary endpoint.

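### The SAP's code for the Mann-Whitney test groups by treatment and centre, so it does not match the two-group treatment comparison that the text names (minor)

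*SAP*

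**What the plan says.** **The test in words.** Protocol 9.4.4: "In case of serious deviations from the normality assumptions, treatments may additionally be compared by a non-parametric test", with the Mann-Whitney U test named in brackets. SAP 2.5.4: "In case of deviations from the normality assumptions, treatments may additionally be compared by a non-parametric test", again naming Mann-Whitney. SAP 5.4.1, directly above the code: "treatments will additionally be compared by a non-parametric test (Mann-Whitney-U-test". None of the three mentions centre in connection with this test.

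**The test in code.** SAP 5.4.1 calls "proc NPAR1WAY data=a wilcoxon", followed by "class TRTN CENTRE", VO2peak as the analysis variable, and an EXACT statement for the Wilcoxon test. There is no STRATA statement. A note explains the variable: "here VO2peak variable contains change from baseline to Week X".

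**The ANCOVA code.** The same class line stands in the PROC MIXED step earlier in 5.4.1. It fits there, because SAP 2.5.2 has treatment and centre as factors.

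**Reuse.** SAP 5.4.2: "Key secondary endpoint will be analyzed similarly to the primary endpoint". With the week left open in the note, the same step would serve week 6.

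**The concern.** A Mann-Whitney test compares two groups, and this trial has two arms. A class line with two variables, one of them having up to about 40 levels, does not describe two groups. A programmer who follows the SAP code would not be following the SAP text, and would have to decide alone what to do with centre. The check would be run only when the primary model's assumptions are in doubt, so the choice should be fixed before unblinding.

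The condition for running the test also varies. SAP 2.5.4 says *may* and SAP 5.4.1 says *will*. The protocol says *may*, and only for *serious* deviations, a word that both SAP sentences drop. Read on its own, the SAP does not say whether the test is optional or required.

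**Working it through.** **1. The plan's own figure.** Inputs from Protocol 9.7 and SAP 3: difference 1.5, SD 3, two-sided 5%, power 90%. The normal approximation gives n = 2 × (1.960 + 1.282)² × 3² / 1.5² ≈ 84.1, so 85 per arm. With the noncentral t distribution, power is 0.8999 at 85 and 0.9032 at 86. The stated 86 per arm is reproduced. It does not depend on the code at issue.

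**2. Text against code.**

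| Place | Test | Groups |
|---|---|---|
| Protocol 9.4.4 | Mann-Whitney U | treatments (2) |
| SAP 2.5.4 | Mann-Whitney U | treatments (2) |
| SAP 5.4.1, sentence | Mann-Whitney U | treatments (2) |
| SAP 5.4.1, NPAR1WAY code | Wilcoxon, exact | treatment and centre |

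Only the last row differs. SAP 4, which lists changes to protocol-specified analyses, does not mention this test.

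**3. How many groups the code would imply.** Protocol 4 gives up to approximately 40 sites. Two arms by 40 centres is 2 × 40 = 80 possible groups. With 200 patients that is 200 / 80 = 2.5 per group. When patients fall at random into 40 equally likely centres, about 74 groups are non-empty, or 200 / 74 ≈ 2.7 patients each.

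**4. What that reading would cost.** This is an illustration, because the documents do not say how the line would be executed. Assumptions: 100 per arm; 40 equally likely centres; no centre effect; normal data; SD 3 at each visit; difference 1.5; two-sided 0.05. The baseline-to-follow-up correlation r is not given, so a range is shown. The SD of change is 3 × √(2(1 − r)).

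The code asks for an exact test, and with fewer than 3 patients per group a large-sample chi-square p-value would be unreliable. The many-group rank statistic (Kruskal-Wallis) was therefore given a permutation p-value. With no treatment difference, at r = 0.5, a run of 1,500 simulated trials with 400 permutations each rejected 0.057 of the time, close to nominal.

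| r | SD of change | Two-group Mann-Whitney | Treatment-by-centre groups, permutation p |
|---|---|---|---|
| 0.3 | 3.55 | 0.83 | 0.14 |
| 0.5 | 3.00 | 0.92 | 0.20 |
| 0.7 | 2.32 | 1.00 | 0.34 |
| 0.8 | 1.90 | 1.00 | 0.55 |

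The run with 400 permutations gave 0.15 / 0.20 / 0.37 / 0.55 for the last column, so these figures are good to about 0.03. If the planned SD of 3 was meant for the change itself, the r = 0.5 row applies. The entry limit on baseline VO2peak (at most 18 ml/min per kg) was not modelled.

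**5. What is unaffected.** The primary ANCOVA has its own step, in which the class line is right. The ordered test of month 3 and then week 6 (SAP 2.6.2) rests on that ANCOVA.

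**The case against.** **The text is clear and the slip is harmless.** All three sentences name the same two-group test. The identical line in the PROC MIXED step points to a copy-over, though that is an inference. If the step stopped with an error, a programmer would notice at once. This stands, and it is why the point is minor. It does not make the code right.

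**The outcome depends on the software.** A reader might infer that the step must fail, or that it cannot give the two-group test under any reading. The documents do not support so absolute a claim. Whether the procedure rejects the second class variable, groups by it or ignores it is a matter of SAS behaviour that they do not describe. If centre were ignored, the named test would result. What the documents do support is that code and text disagree. The power figures apply only to the grouping reading.

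**Perhaps a centre-stratified rank test was meant.** Centre is in the primary model, so this is a tempting inference. But no section names such a test and the step has no STRATA statement. The documents give no ground for attributing that intention to the plan, or for asking for a different rank method in place of the one named.

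**The protocol wording governs anyway.** The SAP introduction says "Data will be analyzed according to the data analysis section 9 of the study protocol", and SAP 4 lists no change here. A reader might conclude that the protocol's condition overrides both SAP sentences. That is an inference: the same introduction says the SAP also covers planned specifications and deviations. The firm point is narrower, namely that the SAP's two sentences disagree with each other.

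**Conclusion.** The concern holds as a minor defect. The class line in the NPAR1WAY step of SAP 5.4.1 does not define the two treatment groups that the sentence above it, SAP 2.5.4 and Protocol 9.4.4 say are to be compared. It is wrong as written, and nothing elsewhere corrects it.

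The effect on the trial's conclusions is small, because the test is supportive and is run only if normality is in doubt. A reader might infer that the primary or key secondary result is at risk; it is not, since neither confirmatory test uses this step. The loss of power applies only if the line were executed as treatment-by-centre groups, and it rests on the assumed correlation, 40 equally likely centres and no centre effect. Its direction is the same at every correlation shown.

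The mismatch between *may* and *will* is a real but separate wording fault of the same minor weight.

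**What to change.** - In the NPAR1WAY step of SAP 5.4.1, change the class line to `class TRTN;`. Use the corrected step for month 3 and wherever it is reused for week 6 under SAP 5.4.2. Leave the class line in the PROC MIXED step as it is.
- Give SAP 2.5.4 and SAP 5.4.1 one and the same condition for running the test. Taking over the wording of Protocol 9.4.4 (serious deviations, *may*) is simplest. If the sponsor wants a different condition, state it in both places and list it in SAP 4.

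Cost: one word removed from the code and two sentences aligned, before unblinding. With the protocol's wording, no protocol amendment is needed. There is no effect on data collection, patients or sample size.
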